## 407 **11 Subgroup Analyses**

408 Descriptive analyses of all safety, HbA1c, 24 hr-CGM and insulin outcomes will be performed  
409 within age groups (6-12, 14-17, 18-25, 26-49,  $\geq 50$ ). Additionally, time in range 70-180 mg/dL  
410 and time  $< 54$  mg/dL during lead-in and treatment periods will be compared within the following  
411 subgroups:

- 412 • Age
- 413 • Diabetes duration
- 414 • Education
- 415 • Sex
- 416 • Race/Ethnicity

- 417 • HbA1c at Screening
- 418 • Pre-study CGM time in range 70-180 mg/dL
- 419 • Humalog lead-in total daily insulin

420 For each subgroup the mean difference and 95% CI will be reported within each group.  
421 Interactions between the subgroup and change from the lead-in to treatment period will be  
422 assessed using repeated measures mixed effects linear regression models with subgroup, visit,  
423 and a subgroup by visit interaction term included as fixed effects and clinical site included as a  
424 random effect. If the subgroup variable is measured on a continuous scale, then the continuous  
425 version will be included in the model. Two-sided p-values for interaction will be reported.

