### 152 2.1 Participant Recruitment and Enrollment

153 Enrollment will proceed with the goal of having up to 200 participants commencing the treatment period  
154 so that at least 160 participants complete the trial (approximately 80 participants age 6-<14 years of age,  
155 and approximately 80 participants age 14+). At least 20 participants will be age 14-<18 years of age.  
156 A maximum of 200 individuals may be enrolled into screening (ie, be consented) in the study in order  
157 to achieve this goal.

158 Study participants will be recruited from ~10-15 clinical centers in the United States without regard to  
159 gender, race, or ethnicity. There is no restriction on the number of participants to be enrolled by each site  
160 toward the overall recruitment goal.

161 In addition, there will be a study-wide goal to have at least 1/3 of completers with baseline HbA1c  $\geq 7.5\%$ ;  
162 and at least 10 completers with basal insulin rate  $>3$  units/hour (for at least part of the day).

163 Enrollment will be staged, starting with the 14+ cohort. After a cumulative 10,000 hours of use are  
164 reached in the age 14+ cohort, a Trial Level Safety Review of all adverse events and device issues will be  
165 performed before opening enrollment to the 6-13 year old cohort. Participants in this review will include  
166 the Medical Monitor, Sponsor personnel, and a medical representative from Eli Lilly. The decision to  
167 proceed with enrollment of younger participants will be driven by the totality of the safety data including  
168 any relevant device or drug  
169 data.

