## 200 **2.2 Participant Eligibility Criteria**

### 201 **2.2.1 Inclusion Criteria**

202 Individuals must meet all of the following inclusion criteria in order to be eligible to participate in the  
203 study.

- 204 1. Age 6 to <81 years
- 205 2. Diagnosis of type 1 diabetes for at least 1 year
- 206 3. Currently using Control-IQ technology for at least 3 months, with CGM data recorded indicative  
207 of system use (active closed loop) for at least 85% of the possible time in 14 days prior to  
208 enrollment
- 209 4. Total daily insulin dose (TDD) at least 2 U/day
- 210 5. HbA1c < 10.5%
- 211 6. Residing full-time in the United States, with no anticipated travel outside the United States during  
212 the period of study participation.
- 213 7. For participants <18 years old, living with one or more parent/legal guardian knowledgeable  
214 about emergency procedures for severe hypoglycemia and able to contact the participant in case  
215 of an emergency, and willing to use the Dexcom Follow app (with push notifications turned on)  
216 for the duration of the study.
- 217 8. If >18 years old, participant has someone who lives within 30 minutes of them who is willing to  
218 be contacted if the study team can't reach the participant in case of a suspected medical  
219 emergency.
- 220 9. Participant has agreed to participate in the study; and has read, understood and signed the  
221 informed consent form (ICF) and assent, if applicable; and has agreed to follow all study  
222 procedures, including:
  - 223 • suspending use of any personal CGM for the duration of the clinical trial once the study  
224 CGM is in use
  - 225 • switching to or continuing to use Humalog during the lead-in period
  - 226 • switching to Lyumjev for the main study period.
  - 227 • willing and able to perform the study exercise and meal challenges.
- 228 10. Investigator has confidence that the participant can successfully operate all study devices and is  
229 capable of adhering to the protocol, including ability to respond to alerts and alarms, and to  
230 provide basic diabetes self-management.
- 231 11. Participant and/or parent/legal guardian have the ability to read and understand English

232 **2.2.2 Exclusion Criteria**

233 Individuals meeting any of the following exclusion criteria at baseline will be excluded from study  
234 participation.

- 235 1. More than 1 episode of diabetic ketoacidosis (DKA) in the past 6 months

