## 38 **4 Sample Size**

39 A sample size of 160 completers was determined to provide reasonable precision for assessing  
40 safety endpoints and is not based on statistical principles. Up to 200 participants will be enrolled  
41 in the trial so that at least 160 complete the trial. We will aim to enroll approximately 80  
42 participants between 6 and 13 years old and approximately 80 participants ages 14 and older,  
43 with at least 20 participants between 14 and 17 years old. A study wide goal will aim to have at  
44 least 33% of trial completers with a screening HbA1c  $\geq 7.5\%$  and at least 10 completers with a  
45 baseline insulin rate  $>3$  units/hour.

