## 274 **8 Statistical Analyses**

### 275 **8.1 Key Safety Analyses**

276 The total number of events, number and proportion of participants who experienced at least one  
277 event during the treatment period and the rate of events per 100 person years will be tabulated  
278 for each outcome listed in Section 5.1. The proportion of SH and DKA events will be compared  
279 to proportions of events occurring in a similar time frame among participants enrolled in the T1D  
280 exchange. These proportions have been previously published [2].

281 Barnard's exact test will be used to test the difference in proportions. A two-sided p-value testing  
282 the null hypothesis of no difference in proportions will be reported. For unanticipated adverse  
283 device effects, adverse drug reactions, and serious adverse events, the total number, number and  
284 proportion of participants who experienced at least one event during the treatment period and the  
285 rate of events per 100 person years will be tabulated.

286 All analyses described in this section will be repeated restricting to only severe hypoglycemic  
287 events that were associated with a seizure or loss of consciousness. Summary statistics will be  
288 reported for key safety outcomes by age group (6-13, 14-17, 18-25, 26-49,  $\geq 50$ ).

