### 289 **8.2 Secondary Safety Analyses**

290 The total number of any type of adverse event, number and proportion of participants who  
291 experienced at least one adverse event during the treatment period and the rate of adverse events  
292 per 100 person years will be tabulated. For the CGM metrics listed in Section 5.2, summary  
293 statistics for each metric will be reported during the pre-study, lead-in, and treatment periods.

294 The main analyses will compare metrics from the lead-in period to the treatment period, and  
295 additional analyses will compare the pre-study period to the treatment period. Linear mixed  
296 models including study visit as a fixed effect and clinical site as a random effect will be used to  
297 estimate the mean change from the lead-in period to the treatment period. Similar models will be  
298 used to estimate the change from the pre-study period to the treatment period. A point estimate,  
299 two-sided 95% confidence interval and two-sided p-value will be reported from the models. If  
300 residuals are highly skewed, then a transformation or non-parametric method will be used.  
301 Summary statistics for all secondary safety endpoints will be tabulated separately for pediatric  
302 and adult participants, and by more detailed age groups (6-13, 14-17, 18-25, 26-49,  $\geq 50$ ).

303 **8.3 Exploratory Analyses**

304 Linear mixed models including study visit as a fixed effect and clinical site as a random effect  
305 will test the change from the lead-in period to the treatment period for all exploratory CGM,  
306 insulin, and HbA1c endpoints. If a central lab HbA1c is not available at baseline the screening  
307 HbA1c will be used. Similar models will test the change from screening to the end of the  
308 treatment period for patient reported endpoints. A point estimate, two-sided 95% confidence  
309 interval and two-sided p-value will be reported from the models. If residuals are highly skewed,  
310 then a transformation or non-parametric method will be used. For CGM metrics, a similar model  
311 will be used to test differences between the pre-study period and the treatment period. All  
312 analyses will be replicated for daytime, nighttime, and postprandial CGM metrics. A sensitivity  
313 analyses will compare all 24 hour CGM metrics between the lead-in and treatment periods  
314 restricting to complete cases. Summary statistics for all exploratory endpoints will be tabulated  

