315 separately for pediatric and adult participants and by more detailed age groups (6-13, 14-17, 18-  
316 25, 26-49, ≥50).

317 **8.4 Meal and Exercise Challenges**

318 Linear mixed models similar to those described in Section 8.3 will be used to test the change  
319 from the lead-in period to the treatment period in CGM and insulin metrics calculated during  
320 meal challenges where no bolus was taken. Summary statistics will be reported for metrics  
321 calculated during meal challenges where a half or full bolus was taken. The percentage of meal  
322 or exercise challenges with a hypoglycemic event will be calculated, but the % time <54 mg/dL  
323 and % time <70 mg/dL will not be computed due to the short timeframe. A similar model will  
324 compare metrics between the lead-in and treatment periods for exercise periods, and linear  
325 contrasts will be used to test the null hypotheses that metrics for all 3 exercise periods during the  
326 treatment period are not different from the metrics calculated during lead-in period. For binary  
327 outcomes, repeated measures logistic regression model will be used to compare lead-in and  
328 treatment periods. Summary statistics for all meal and exercise challenge endpoints will be  
329 tabulated separately for pediatric and adult participants and by more detailed age groups (6-13,  
330 14-17, 18-25, 26-49, ≥50).

331 **8.5 Protocol Adherence and Retention Analysis**

332 The following outcomes relating to protocol adherence and retention will be reported. Summary  
333 statistics appropriate to the distribution will be tabulated.

- 334 • A flowchart reporting the following:
  - 335 ○ Number of participants enrolled
  - 336 ○ Number of participants who completed the Humalog training visit
  - 337 ○ Number of participants who completed the Lyumjev training visit
  - 338 ○ Number of participants who completed/missed the 6-week visit
  - 339 ○ Number of participants who completed/missed the 13-week visit
  - 340 ○ Number of participants who dropped from the study between each visit
- 341 • Reasons for dropouts
- 342 • Number of protocol deviations

- 343 • Number of and reasons for unscheduled visits and contacts

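### The age bands in SAP section 11 skip age 13, so the age-group tables specified there omit 13-year-olds, in conflict with the 6-13 band used in SAP sections 8.1 to 8.4

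*SAP*

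**What the plan says.** The first sentence of SAP section 11 sets the scope: "Descriptive analyses of all safety, HbA1c, 24 hr-CGM and insulin outcomes will be performed". It then gives the bands, "within age groups (6-12, 14-17, 18-25, 26-49" and 50 or older). Next, section 11 asks for time in range 70-180 mg/dL and time below 54 mg/dL to be compared between lead-in and treatment within several subgroups. Age is the first of these, and a mean difference and 95% CI are to be reported in each group. It does not say which age bands those estimates use.

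Elsewhere the SAP starts its bands at 6-13:

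- Section 8.1, key safety: "reported for key safety outcomes by age group (6-13, 14-17, 18-25, 26-49" and 50 or older).
- Section 8.2, secondary safety: "and adult participants, and by more detailed age groups (6-13, 14-17, 18-25, 26-49" and 50 or older).
- Section 8.3, exploratory endpoints: "separately for pediatric and adult participants and by more detailed age groups (6-13, 14-17" and onward with the same upper bands.
- Section 8.4, meal and exercise challenges: the same five bands.

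Age 13 is part of the trial. Protocol section 2.2.1 admits "Age 6 to <81 years". Protocol section 2.1 plans "approximately 80 participants age 6-<14 years of age" as the younger cohort, and SAP section 4 describes the same split as "participants between 6 and 13 years old and approximately 80 participants ages 14 and older".

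**The concern.** The first two bands in section 11 are not adjacent. One ends at 12 and the next begins at 14, with no reason given for leaving out the year between. This is an instruction to a programmer, not background text. Followed literally, it produces age-group rows that do not add up to the total, and a youngest group with a different denominator from the one in the section 8 tables for the same outcomes.

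Section 11 also asks for something that section 8 does not. Section 8 specifies only summary statistics by age group. The within-group mean change with a 95% CI, for time in range and for time below 54 mg/dL, appears only in section 11. If those estimates take the bands printed a few lines above them, 13-year-olds drop out of the only age-specific change estimates in the plan.

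**Working it through.** No sample size, power or error-rate figure is involved. The check is whether each set of bands covers every eligible age, and then how many participants the gap could involve.

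**Coverage.** Eligible ages in whole years run from 6 to 80, which is 80 − 6 + 1 = 75 years. The top band (50 or older) therefore spans 50 to 80, or 31 years.

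| Source | Bands | Years covered | Uncovered |
|---|---|---|---|
| SAP section 11 | 6-12, 14-17, 18-25, 26-49, ≥50 | 7 + 4 + 8 + 24 + 31 = 74 | 75 − 74 = 1 (age 13) |
| SAP sections 8.1 to 8.4 | 6-13, 14-17, 18-25, 26-49, ≥50 | 8 + 4 + 8 + 24 + 31 = 75 | none |
| SAP Table 1 (registry) | 6-12, 13-17, 18-25, 26-49, ≥50 | 7 + 5 + 8 + 24 + 31 = 75 | none |

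No set has overlaps. The section 11 list has the first band of the registry scheme and the second band of the trial scheme. Each scheme is complete by itself, but the combination is not.

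**Number affected.** The inputs are about 80 participants aged 6 to 13 and 160 completers in all (Protocol sections 2.1 and 8.3, SAP section 4). The share aged 13 is not given, so it is assumed.

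- Even spread over the eight years 6 to 13: 80 × 1/8 = 10, which is 12.5% of the younger cohort and 10/160 = 6.25% of completers.
- Share of 5%: 80 × 0.05 = 4, or 4/160 = 2.5% of completers.
- Share of 20%: 80 × 0.20 = 16, or 16/160 = 10% of completers.

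Under the even spread, the youngest row in section 11 would hold 80 − 10 = 70 participants where section 8 has 80, and the section 11 rows would sum to 160 − 10 = 150.

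**Where 13-year-olds remain.**

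- Key safety by age: section 8.1, with the 6-13 band.
- Reportable adverse events and CGM hypoglycemia by age: section 8.2, with the 6-13 band.
- Exploratory CGM, HbA1c and insulin outcomes by age: section 8.3, with the 6-13 band.
- Pooled analyses and the pediatric summaries: no gap.
- Registry comparison: section 6.1 splits at 18 years, so no gap.
- Interaction test for age: section 11 enters a continuous subgroup variable as continuous, so age 13 stays in the model.

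**Effect of the correction.** With 6-13 as its first band, section 11 covers 75 of 75 years with no overlap.

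**The case against.** The best defense is that this is a typing slip in a largely duplicate table. Every outcome class named in the opening sentence of section 11 is already tabulated in sections 8.1 to 8.3 with the 6-13 band, and the affected sentence asks only for description. A row labelled 6-12 reports ages 6 to 12 correctly, and anyone adding the rows would see that they fall short of the total. Nor does the SAP say that the age-subgroup mean differences must use the printed bands. All of this stands, and it limits the consequence. It does not remove the conflict: a programmer cannot satisfy sections 8 and 11 with one table, and nothing in section 11 supplies other bands for the age estimates.

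A reader might infer three stronger things that the documents do not support.

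- That 13-year-olds disappear from the trial's age reporting. They do not, given the section 8 tables, the pediatric summaries and the continuous-age model.
- That pediatric events are understated. The pediatric summaries have no gap. The most that can be said is that an event in a 13-year-old would appear in no section 11 age row.
- That safety oversight of the younger cohort is weakened. Under Protocol section 2.1, the Trial Level Safety Review uses data from the cohort aged 14 and older, before the younger cohort opens. SAP section 12 sets its content without the section 11 bands. The pediatric suspension rule in Protocol section 6.6.2 counts cases across all pediatric participants.

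**Conclusion.** The gap is real, and it is confined to section 11. Exactly one eligible year of age has no band, in conflict with sections 8.1 to 8.4 and with the enrollment cohort. The number omitted from the descriptive age tables is about 10 of 80 under an even spread and 4 to 16 under a share of 5% to 20%. Both rest on assumed age distributions and on the completer target of about 80, so the count would change in proportion if the cohort analyzed were larger or smaller. Whether the section 11 mean differences and 95% CIs by age are also affected depends on the bands used for them, which the SAP does not state.

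No hypothesis test against the registry, success criterion, sample size, safety review or stopping rule changes. This is a minor but unambiguous error in an analysis instruction, most likely a slip, and worth correcting because it can be programmed as it stands.

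**What to change.** In SAP section 11, change 6-12 to 6-13, and add a sentence saying that the age-subgroup mean differences and CIs use the same five bands. The registry split of 6-12 and 13-17 would also close the gap, but it does not match the 6-13 and 14-and-older cohorts or the section 8 tables, so 6-13 is the better choice.

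The edit is one character plus one clarifying sentence and needs no new data. SAP version 4.0 is listed as effective when enrollment and follow-up were complete, so the change should be recorded as a correction of an internal inconsistency. Any section 11 age tables already run with the printed bands should be rerun.

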## 426 **12 Trial Level Safety Review**

427 A trial level safety review will be conducted when participants have been followed for a  
428 combined 10,000 hours. Summary statistics will be tabulated for key safety endpoints listed in  
429 Section 5.1, device issues (Section 10.1), and infusion site reactions (Section 10.2). Listings with  
430 descriptions of each event will be provided.

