Number of Participants	
Up to 200 participants commencing treatment period so that at least 160 complete study (at least 80 participants age 6-<14 years old, and at least 80 participants age 14+). At least 20 participants will be age 14-<18 years of age.
 
 
• Goal to have at least 1/3 of all completers with HbA1c <math>\geq 7.5\%</math>
 
• Goal to have at least 10 completers with basal insulin rate >3 units/hour (for at least part of the day)
 
 
Enrollment will be staged, starting with the 14+ cohort. After a cumulative 10,000 hours of use are reached in the age 14+ cohort, a Trial Level Safety Review of all adverse events and device issues will be performed before opening enrollment to the 6-13 year old cohort.

Participant Population:	
Eligibility to enroll in the study will be assessed based on the following inclusion criteria:
 
 
1. Age 6 to <81 years
 
2. Diagnosis of type 1 diabetes for at least 1 year
 
3. Currently using Control-IQ technology for at least 3 months, with system use (active closed loop) for at least 85% of the possible time in 14 days prior to enrollment
 
4. Total daily insulin dose (TDD) at least 2 U/day
 
5. HbA1c < 10.5%
 
6. Residing full-time in the United States, with no anticipated travel outside the United States during the period of study participation.
 

PARTICIPANT AREA	DESCRIPTION

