### 707 **6.2.4 Hyperglycemic/Ketotic Events**

708 Hyperglycemia not associated with an Adverse Device Effect or discontinuation of the study device or  
709 study drug is only reportable as an adverse event when one of the following criteria is met:

- 710 • the event involved DKA, as defined by the Diabetes Control and Complications Trial (DCCT)  
711 and described below
- 712 • evaluation or treatment was obtained at a health care provider facility for an acute event involving  
713 hyperglycemia or ketosis, or the participant contacted the site and received guidance on how to  
714 manage the hyperglycemia/ketosis
- 715 • blood ketone level  $\geq 1.0$  mmol/L, even if there was no communication with a health care provider  
716 at the time of the event

717 Hyperglycemic events are classified as DKA if the following are present:

- 718 • Symptoms such as polyuria, polydipsia, nausea, or vomiting;
- 719 • Serum ketones  $>1.5$  mmol/L or large/moderate urine ketones;
- 720 • Either arterial blood pH  $<7.30$  or venous pH  $<7.24$  or serum bicarbonate (or CO2)  $<15$ ; and
- 721 • Treatment provided in a health care facility

722 When a hyperglycemia/ketotic event qualifies as an SAE as defined in section 6.2.1, a Hyperglycemia/  
723 DKA Form should be completed in addition to the Adverse Event Form. Events meeting DKA criteria  
724 should be considered to be serious adverse events with respect to reporting requirements. Hyperglycemia  
725 events not meeting criteria for DKA generally will not be considered as serious adverse events unless one  
726 of the SAE criteria in section 6.2.1 is met.

727 When a hyperglycemia/DKA event occurs during use of a study device, it generally will be considered to  
728 be unrelated to the device (per section 6.2.6) if the device functioned as intended and there does not  
729 appear to be a flaw in how the device is intended to function.

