## 46 **5 Endpoints**

### 47 **5.1 Key Safety Endpoints**

- 48 • Severe hypoglycemia
- 49 • Diabetic ketoacidosis
- 50 • Unanticipated adverse device effects (UADE)
- 51 • Other serious adverse events
- 52 • Adverse drug reactions

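### SAP Section 12 compiles a narrower set of events than the protocol requires for the safety review that opens enrollment to ages 6-13

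*SAP*

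**What the plan says.** The protocol summary states that, once the 14+ cohort has accumulated 10,000 hours of use, "a Trial Level Safety Review of all adverse events and device issues will be performed before opening enrollment to the 6-13 year old cohort". Protocol Section 2.1 repeats this scope ("a Trial Level Safety Review of all adverse events and device issues will be" performed). It names the participants as the Medical Monitor, Sponsor personnel and a medical representative of the insulin manufacturer, and says the decision to proceed will be "driven by the totality of the safety data including" relevant device or drug data.

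SAP Section 12, added in SAP version 2.0 for this review, gives the trigger and content as "combined 10,000 hours. Summary statistics will be tabulated for key safety endpoints listed in" "Section 5.1, device issues (Section 10.1), and infusion site reactions (Section 10.2). Listings with" "descriptions of each event will be provided". Section 5.1 holds severe hypoglycemia, DKA, unanticipated adverse device effects, other serious adverse events and "Adverse drug reactions". All reportable adverse events appear as a separate endpoint in Section 5.2, which Section 12 does not cite. SAP Section 1 declares every analysis in the SAP consistent with the protocol.

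Protocol Sections 6.2.3 and 6.2.4 define which milder glycemic events are reportable. They include events evaluated at a health care facility, events for which the site gave guidance, and a blood ketone level of 1.0 mmol/L or more, "even if there was no communication with a health care provider" at the time.

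**The concern.** The protocol asks for all adverse events. The SAP prepares a subset, chosen by seriousness, by attribution to the drug or device, or by being a site reaction. The review is the one staged-enrollment decision in the trial, and it concerns the youngest participants. If Section 12 is followed as written, the reviewers' compiled package would not show how many milder ketotic, hyperglycemic or hypoglycemic events had been reported, unless each had been attributed to the drug or device. The serious endpoints that are tabulated have little exposure behind them at that stage.

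**Working it through.** **Step 1: compare the two scopes.**

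- Protocol: every adverse event, plus device issues.
- SAP Section 12: severe hypoglycemia, DKA, unanticipated device effects, other serious events, adverse drug reactions, device issues and infusion site reactions.
- Difference: reportable events that are non-serious, not attributed to the drug, not a device effect or device issue, and not a site reaction.

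Ketones of 1.0 mmol/L or more without DKA can fall in that difference. So can hypo- or hyperglycemia managed with site guidance or at a facility without meeting a serious criterion. Two protocol rules make this realistic. Section 6.2.4 says hyperglycemia/DKA events are generally considered unrelated to the device if it worked as intended. Section 6.2.1 reserves the term adverse reaction for events caused by a drug, a stricter standard than a suspected reaction.

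The listings in Section 12 follow directly on the named categories. Their natural reading is a description of each event in those categories.

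**Step 2: exposure at the review.** The documents give no expected event count or precision for it, so there is no stated figure to reproduce.

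- 10,000 / 24 = 416.7 days.
- 416.7 / 365.25 = 1.14 person-years.
- 416.7 / 91 = 4.58 thirteen-week periods.
- Against 80 participants followed for 91 days: 416.7 / 7,280 = 5.7%.

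**Step 3: chance of seeing no event.** With p the three-month proportion in the overall rows of SAP Table 1, P(none) = (1 - p)^4.58. The age bands from 13 up are the nearest match to the 14+ cohort.

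| Age band | Severe hypoglycemia | P(none) | DKA | P(none) |
|---|---|---|---|---|
| 13-17 | 155/3183 = 4.87% | 80% | 113/3183 = 3.55% | 85% |
| 18-25 | 138/2445 = 5.64% | 77% | 96/2445 = 3.93% | 83% |
| 26-49 | 157/2143 = 7.33% | 71% | 43/2143 = 2.01% | 91% |
| 50 and over | 189/1976 = 9.56% | 63% | 22/1976 = 1.11% | 95% |
| Pooled | 639/9747 = 6.56% | 73% | 274/9747 = 2.81% | 88% |

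The CGM-user rows give 73-89% for severe hypoglycemia and 91-99% for DKA. At the pooled overall rates, the chance that both are zero is (0.9344 x 0.9719)^4.58 = about 64%, assuming independence.

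**Step 4: what a zero would show.** With no events, the one-sided 95% upper limit is 2.996 / 1.14 = about 2.63 per person-year, or 263 per 100 person-years. The pooled registry proportion for severe hypoglycemia implies -ln(1 - 0.0656) x 4.58 = 0.31 expected events. Dividing by 1.14 gives about 27 per 100 person-years. A clean result would therefore leave rates up to more than nine times the registry's unexcluded.

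**The case against.** The strongest reply is that Section 12 lists what will be tabulated and does not limit what the reviewers may see. Protocol Section 2.1 sets the scope of the review. Under Section 6.5 the Medical Monitor reviews every reported adverse event and the Sponsor is informed of all of them, so two of the three parties already receive them. That stands, and it reduces the weight of the point. It does not give the manufacturer's representative the same information, and individual reports are not a compiled table. It also leaves SAP Section 1's claim of consistency incorrect here.

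The omitted set also depends on attribution. A hypoglycemic event judged drug-related would count as an adverse drug reaction, and Section 6.3 sends adverse device effects to the device issue form as well, apart from minor skin reactions. This is accepted: only the remainder is missing.

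A reader might infer several stronger things that the documents do not support:

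- *That the reviewers would mostly be shown zeros.* The package includes non-serious adverse drug reactions, site reactions of every severity, occlusion alarms that prompted a set change, and device issues. No rate is given for these. If one such category ran at an assumed 100 events per 100 person-years, the chance of none would be exp(-1.14) = 32%; at an assumed 400 it would be exp(-4.56) = 1%.
- *That the omitted events are the more frequent ones, or that the ketone threshold was set as a warning signal.* The documents give no such rate and no such purpose. The threshold is only a reporting criterion.
- *That nothing else protects the children.* Section 6.6.2 has a study-wide suspension rule (5 cases of severe hypoglycemia, or 5 serious hyperglycemic/ketotic events) and a pediatric rule (3 of either). Section 6.5 adds continuing review of events and periodic review of compiled data.

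Finally, SAP version 4.0 is dated after enrollment and follow-up were complete, so editing it cannot alter a decision already taken. That is fair, and the remedy has to allow for it.

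**Conclusion.** The inconsistency is real and visible on the page. The protocol requires all adverse events; SAP Section 12 leaves out the Section 5.2 endpoint that would supply them. The consequence is an incomplete compiled package, not proof that anyone decided without the information. It deserves correction because the rare endpoints say little at 1.14 person-years: about 63-80% chance of no severe hypoglycemia and 83-95% of no DKA.

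These figures assume that registry rates apply to the cohort and that all 10,000 hours are treatment-period exposure. Table 1 counts severe hypoglycemia only with seizure or loss of consciousness. The study counts any altered consciousness needing another person's active help, so the first range may be somewhat overstated. Lower rates among CGM users push the other way. The scope mismatch itself rests on none of these assumptions.

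**What to change.** In SAP Section 12, add the tabulation and listing of all reportable adverse events (Section 5.2), with ketotic/hyperglycemic events and hypoglycemic events on separate lines. If the review has already taken place, record in the study file whether all adverse events were presented to it.

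The cost is one sentence in the SAP and one more table and listing from data already collected. No visits or participants are added.
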